The concept of SDM goes back to 1972, before a landmark paper identified the four key components still found in modern definitions: (a) involvement of at least two parties, usually physician and patient, (b) sharing of information, (c) physician and patient both taking steps to participate in the decision making, and (d) agreement on the decision.(1) The shift in how we deliver patient centred care and the ethical imperative underpinning SDM is clearly reflected in the 2012 Health and Social Care Act and the "Liberating the NHS: 'No decision about me without me" guidance.(2) While the mandate for SDM is clear, there is still a notable evidence gap with no research addressing the impact of implementing SDM in UK emergency medicine (EM).

A priority setting partnership (PSP) between the Royal College of Emergency Medicine (RCEM) and the James Lind Alliance ranked the question on chest pain investigation strategies alongside SDM sixth, highlighting the SDM component as the main priority for future research.(3)

Through the Greater Manchester T-MACS initiative, T-MACS has become one of the country's leading algorithms for patients presenting to the ED with suspected cardiac chest pain. T-MACS was derived by our group using a logistic regression model that provides the treating physician with a probability of their patient having ACS. This patient specific probability incorporating details the patient's symptoms, electrocardiographic (ECG) findings and a single cardiac troponin concentration measured on arrival in the ED can be used to inform clinical decision making.(4) However, even with modern prediction models like T-MACS and advances in cardiac troponins, the large numbers of patients presenting to the ED with chest pain remain a challenge, partially explained by physicians being fairly risk averse. Research into what is considered acceptable risk demonstrated that only 4 out of 10 ED physicians would accept a 1% risk of a major adverse cardiac event (MACE) at 30 days when taking the sole responsibility in making decisions.(5)

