5.2 Study Intervention and/or Procedures

We will undertake a stepped wedged cluster randomised controlled feasibility trial at two emergency departments (representing individual clusters): Manchester Royal Infirmary and the Royal Albert Edward Infirmary Wigan. With no site initially exposed to the shared decision making intervention, they will subsequently cross over after 2 months to intervention with a 1-month transition period for training purpose. The start date for each site will be randomly assigned.

MANCHES

Months	1	2	3	4	5	6	7	8
Trial set up								
Recruitment 1 st centre								
Recruitment 2 nd centre								
Data entry &verification								

Control group: Patients presenting with suspected cardiac chest pain receive diagnostic and treatment interventions according to local emergency department protocols based on T-MACS that have been verified for compliance with national or international guidance and are already in use at both hospitals as part of routine clinical care.

Transition stage: On completion of the recruitment time in the control arm the cluster will enter a designated 1-month transition stage. The purpose of this stage is twofold:

1) to allow installation of an update T-MACS Calculator with integrated SDM feature allowing to print off of the bespoke T-MACS Choice decision aid; and

2) physicians to undergo a designated training session on SDM including theory of the three talk communication model and demonstration of a shared decision making conversation using T-MACS Choice. This teaching session will be delivered as a face to face teaching session lasting 30-45 min by a member of the research team where possible. However, considering ongoing constraints on face-to-face teaching in light of the COVID-19 pandemic the teaching session where necessary will be provided as a live or on-demand online session allowing it to be readily accessible.

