Intervention: We will examine the use of SDM with the previously designed decision aid T-MACS Choice. The treating emergency physician will routinely evaluate the patient as well as review blood tests including an initial troponin result before entering relevant information into the T-MACS calculator. The calculator will generate a personalised decision aid incorporating the calculated probability that the patient has a MACE within 30 days. This will then be used in the SDM conversation following the three-talk model.(15) Patient disposition including serial troponin testing will be decided on in the SDM conversation.

6) STUDY PARTICIPANTS

6.1 Inclusion Criteria:

- Adult patients ≥18 years of age presenting to the ED with:
 - Pain, discomfort or pressure in the chest, epigastrium, neck, jaw or upper limbs
 - No obvious non-cardiac source
 - o Symptoms the treating emergency physicians feels warrant investigation for suspected ACS

6.2 Exclusion Criteria:

- Patients with peak symptoms >12 hours before presenting to the ED
- Patients requiring referral for immediate primary percutaneous coronary intervention due to unequivocal evidence of ST elevation myocardial infarction
- Patients requiring hospital admissions for another medical condition
- Patients that lack mental capacity to provide written informed consent

MANCHESTER 1824

The University of Manchester

 Patients whose level of English does not allow them to participate in the SDM conversation in a meaningful way.

6.3 Recruitment:

Recruiting to research in an emergency setting is always challenging due to combination of factors including a high clinical work load, a proportion of eligible patients presenting out of hours with research teams often not being able to support recruitment and not least patients experiencing this as a stressful high-stake situation. Experience with the targeted patient population presenting with suspected cardiac chest pain captured in a qualitative interview study as part of the original MACS pilot RCT showed that patients often struggle with the concept of formal written informed consent in a situation they perceive as high stakes and they when they are in discomfort.(16)

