However, recruiting a consecutive sample of patients allowing all patients with suspected cardiac chest pain to participate is vital to minimise recruitment bias and make findings generalisable. In this study we therefore plan to recruit 24 hours a day, 7 days per week at both clusters to evaluate our ability to deliver training to physicians in shared decision making and ultimately their ability to deliver the concept using the T-MACS Choice decision aid in clinical care. To achieve this, we will adopt a proportionate opt-out consent process as the risk of harm to patients is negligible. This allows trained clinicians to recruit patients as part of providing routine care with support of the research team in the daytime during weekdays.

This process has specifically been designed to ensure that patients are sufficiently informed and provided with dedicated opportunities to ask questions and engage with the study at their preference and indicate their desire to opt out from all or parts of the research. This study does not change the clinical treatments patients receive. It rather implements communication training to facilitate SDM with the decision aid T-MACS Choice allowing clinicians to communicate available options in a different way. With the strong ethical imperative underpinning SDM (17,18) and the extensive evidence for T-MACS as reliable prediction model, SDM and the decision aid T-MACS Choice will be implemented for all patients with suspected cardiac chest pain at cluster level (in both ED's) regardless of patients participation in the study. Notably, SDM does involve a consensual interaction between physician and patient as one of the core principles. A patient not engaging with the process of SDM is therefore opting out by non-participation.

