To inform patients about the study we will display relevant information in the appropriate areas of the participating ED's describing the study and assuring patients that their clinical care will not be affected in any way regardless of their decision to participate. Patients that have a T-MACS score calculated are considered to meet eligibility criteria of this study as the in- and exclusion criteria are identical with those clinicians use when considering if applying T-MACS is indicated. The individual patient will be offered a patient information sheet (PIS) including a description of the study and a point of contact. PIS documents will be numbered with individual study ID-numbers that will be linked to the T-MACS database that is routinely created on entering the participants clinical data into the T-MACS calculator. The existing T-MACS database will therefore serve as a list of eligible participants while also ensuring that every eligible participant has received a PIS. At the end of each week the T-MACS database will be cross-checked against the patient post-encounter surveys to check for any patients that have opted out and to highlight their opt-out status on potential follow up on a dedicated opt-out log.

The additional interventions that deviate from normal practice patients will undergo, unless they opt-out, is a short post-encounter survey about their experience of the clinical encounter during their initial visit to the ED. Those participants in the SDM group that opt-in for follow up will complete a second survey at 30 days

remotely via telephone or via email linking them to a survey within the Research Electronic Data Capture (REDCap) database. All participants that opt-in for follow up on their clinical outcomes at 30 days will have their GP contacted and their medical records checked by the research team to verify any cardiac events. Participants are free to opt-out or opt-in from all or some of the follow up components as they wish to.

As part of the monitoring process the opt-out log will be cross-referenced with the REDCap database at the end of each month in the recruitment period and upon finishing data collection.

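### A T-MACS score cannot show that the capacity and English exclusions were checked, so the T-MACS database overstates the eligible count by an unknown amount

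*Protocol*

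**What the plan says.** Protocol section 6.3 sets the working eligibility rule: "Patients that have a T-MACS score calculated are considered to meet eligibility criteria of this study". The reason given is that "the in- and exclusion criteria are identical with those clinicians use when considering if applying T-MACS is indicated". It then draws the consequence for counting: "The existing T-MACS database will therefore serve as a list of eligible participants".

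Section 6.2 lists five exclusions. Two of them are:

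- "Patients that lack mental capacity to provide written informed consent"
- "Patients whose level of English does not allow them to participate in the SDM conversation in a meaningful way"

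Three other places bear on whether a score can stand in for these two:

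- Section 3 describes the score as built from symptoms, "electrocardiographic (ECG) findings and a single cardiac troponin concentration measured on arrival in the ED".
- Section 5.2 says of the T-MACS-based local protocols that they "are already in use at both hospitals as part of routine clinical care".
- On the scope of the decision aid, section 6.3 says that it "will be implemented for all patients with suspected cardiac chest pain at cluster level (in both ED's) regardless of patients participation in the study".

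The list of eligible patients feeds the results directly. Section 7 makes the monthly eligible count and the recruitment rate components of the primary outcome. The first green cell of the proceed table in section 17 requires that more than half of eligible patients complete the post-encounter survey.

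**The concern.** The two exclusions are defined by the study's consent and by its intervention, not by whether a risk score is clinically indicated. A clinician can calculate T-MACS for a patient who cannot consent to research or cannot follow the SDM conversation. In the control period there is no SDM conversation, so routine care gives no occasion to judge whether a patient's English would suffice for one. The statement that the criteria are identical therefore conflicts with section 6.2.

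If the rule is followed as written, such patients stand in the database as eligible. Section 6.3 describes a weekly cross-check, but it looks for opt-outs. The protocol describes no exclusion log and no screening step. An excluded patient who returns no survey then looks like an eligible patient who was not recruited.

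The eligible count and the completion rate are main products of a feasibility trial and will be used to plan the definitive one. An error in their shared denominator that the study cannot measure weakens both.

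**Working it through.** **Can a score imply the exclusions?**

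| Exclusion in section 6.2 | Could it be a limit on T-MACS use? |
|---|---|
| Symptom timing; immediate primary PCI; admission for another condition | Plausibly; the protocol does not show otherwise |
| Capacity for written informed consent | No: it concerns research consent, while T-MACS is routine care |
| English sufficient for the SDM conversation | No: T-MACS was in use before SDM was introduced |

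The point rests on the last two rows only.

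**Inputs**

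- Expected eligible patients: about 200-300 per cluster per month (section 9.2). No derivation is given, so there is nothing to reproduce. For illustration I treat it as the number of T-MACS records, N.
- Recruitment: 2 clusters x 4 months (2 control, 2 intervention), so 1,600-2,400 records.
- x, the share of records meeting either exclusion: not in the protocol; **assumed 2-20%**.
- Green line: 50% (section 17).

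**Eligible count.** True eligible = N(1-x), so the recorded count is too high by x/(1-x).

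| x | True eligible per cluster-month | Overstatement | Records wrongly counted, whole trial |
|---|---|---|---|
| 2% | 196-294 | 0.02/0.98 = 2.0% | 32-48 |
| 5% | 190-285 | 0.05/0.95 = 5.3% | 80-120 |
| 10% | 180-270 | 0.10/0.90 = 11.1% | 160-240 |
| 20% | 160-240 | 0.20/0.80 = 25.0% | 320-480 |

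**Completion.** Let t be true completion among eligible patients, and let excluded patients return surveys at r times that rate. Observed completion = t[(1-x) + r·x] = t[1 - (1-r)x]. The true value at which the observed rate equals 50% is 0.50/[1 - (1-r)x].

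| x | True completion needed, r = 0 | True completion needed, r = 0.5 | True 55% reads, r = 0 | True 55% reads, r = 0.5 |
|---|---|---|---|---|
| 2% | 51.0% | 50.5% | 53.9% | 54.5% |
| 5% | 52.6% | 51.3% | 52.3% | 53.6% |
| 10% | 55.6% | 52.6% | 49.5% | 52.3% |
| 20% | 62.5% | 55.6% | 44.0% | 49.5% |

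The 55% is illustrative. With r = 0 it falls below the line once x exceeds 1 - 0.50/0.55 = 9.1%.

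**The two harms trade off.** With r = 0 the rate is diluted most, but no ineligible survey enters the data. With r = 0.5 the dilution roughly halves, and the ineligible share of completers is 0.5x/(1 - 0.5x): 1.0%, 2.6%, 5.3% and 11.1% for the four values of x. Both harms cannot be at their worst together.

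**The case against.** The strongest reply is that this may be a loose word with little effect, and parts of that reply stand.

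- **Size.** The protocol gives no figure for x, and x could be small. At 2% the effect is slight. This stands.
- **Consequences.** The monthly eligible count has no row in the proceed table. Missing green in row 1 leads to adjustment of the protocol, not abandonment, and even a single red may be rectifiable. A diluted completion rate errs on the cautious side. If no excluded patient responds, the number of completed surveys per month is unaffected: at x = 10%, 200 x 0.495 = 180 x 0.55 = 99. All of this limits the harm. It does not make the eligible count or the rate correct, and the count errs on the optimistic side.
- **Enrolment.** A reader might infer that excluded patients are enrolled. The protocol does not show this. Section 6.3 does not repeal section 6.2; clinicians offer the information sheet, the survey has to be actively completed, the follow-up components need an opt-in, and not engaging with SDM counts as opting out. What remains is that opt-out consent without a screening step allows it. The non-engagement rule also cannot work in the control period, and in the intervention period it leaves the patient in the denominator.
- **Calculator use.** A reader might also infer that calculator use changes once it prompts an SDM conversation, or that eligible patients never scored distort the rate by some stated amount. The protocol gives no evidence for the first and no coverage figure for the second. Local protocols at both sites are based on T-MACS, training is mandatory, and T-MACS Choice applies to all suspected cardiac chest pain patients. Neither inference is part of this point.

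**Conclusion.** The contradiction holds for two of the five exclusions. Section 6.3 equates the study criteria with those for applying T-MACS, section 6.2 contains two exclusions that a score cannot establish, and no described step reconciles them. The T-MACS database is therefore not a valid list of eligible patients as it stands.

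The direction for the eligible count is upward. The completion rate is biased downward to the extent that excluded patients respond less often than eligible ones. The size is unknown: the 2-25% overstatement rests wholly on the assumed 2-20% range, and the 51.0-62.5% range for the effective green line also requires that excluded patients return no surveys. Whether the row 1 result would change depends on how near true completion lies to 50%, which cannot be known in advance. The right description is unreliable by an unmeasured amount, rather than shown to be wrong.

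**What to change.** 1. In section 6.3, delete the statement that the study criteria are identical to those for applying T-MACS.
2. In both the control and the intervention period, record two yes/no items for each T-MACS record: capacity to consent, and adequate English. Put them on study paperwork linked by the study ID, such as the numbered information sheet or the paper CRF. The live calculator need not be altered.
3. Define eligible patients as T-MACS records minus documented exclusions. Use that one definition for the monthly eligible count, the recruitment rate and row 1 of the proceed table.

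The cost is two extra fields per patient. In return, x is measured instead of assumed, and the definitive trial can be planned on a denominator that matches its own criteria.

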13.2 Risks

SDM involves presenting patients with the possibility of "doing nothing" which in our study would equate to going home without serial troponin testing. While this intuitively sounds risky and potentially hazardous when thinking of patients identified as having a moderate or high risk of ACS, mentioning the option is merely represents real life options. Offering choice should not be confused with actively advocating for a particular option. Ultimately the choice does and should lie with the patient, as long as it represents an informed decision as this is respecting their autonomy.

14) STATEMENT OF INDEMNITY

The University has insurance available in respect of research involving human subjects that provides cover for legal liabilities arising from its actions or those of its staff or supervised students. The University also has insurance available that provides compensation for non-negligent harm to research subjects occasioned in circumstances that are under the control of the University.

15) FUNDING and RESOURCES

Funding for this study was obtained from the Royal College of Emergency Medicine - RCEM Grant Number: G/2019/3.

16) PUBLICATION POLICY

This study will provide hardly needed evidence on the impact of SDM in UK emergency medicine and more specifically its role in the diagnostic process of patients presenting with suspected cardiac chest pain to the ED.

We will disseminate our findings in a multiple ways to maximise impact and accessibility to a wide audience including: (a) publication in peer reviewed academic journals, aiming for journals with high impact and a relevant target audience; (b) presentation at national and international scientific conferences; (c) publication on the trial and research group websites; (d) dissemination via press releases (including by Central Manchester University Hospitals NHS Foundation Trust; The University of Manchester; the NIHR

MANCH

Clinical Research Network); and (e) to promote public engagement, social media and blog posts. Participants that have indicated an interest in being kept informed will be updated as and when results will become available.

17) PROCEED CRITERIA

Depending on the outcome of the feasibility study the following proceed criteria have been agreed by the Trial Steering Committee:

Green	Yellow	Red
>50% of eligible patients	<25% under target recruitment	>50% under target recruitment
complete post-encounter survey	rate	rate

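### Section 6.3 counts every T-MACS record as an eligible participant, but section 6.2 has exclusions that a T-MACS score does not imply, so the eligible denominator can be wrong

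*Protocol*

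**What the plan says.** Section 6.3 (Recruitment) sets the working rule for eligibility: "Patients that have a T-MACS score calculated are considered to meet eligibility criteria of this study". The reason given is that "the in- and exclusion criteria are identical with those clinicians use when considering if applying T-MACS is indicated". The protocol then draws the consequence: "The existing T-MACS database will therefore serve as a list of eligible participants".

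Section 6.2 (Exclusion Criteria) includes two items that concern the study and not the risk score: "Patients that lack mental capacity to provide written informed consent", and "Patients whose level of English does not allow them to participate in the SDM conversation in a meaningful way".

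Section 5.2 says of the T-MACS-based protocols in the control phase that they "are already in use at both hospitals as part of routine clinical care". It describes the start of the trial in these words: "With no site initially exposed to the shared decision making intervention".

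The list feeds section 7, where the number of eligible participants per month and the recruitment rate are parts of the primary composite. It also feeds section 17, where the first green criterion requires that ">50% of eligible patients" complete the post-encounter survey. Section 9.2 expects about 200 to 300 eligible patients per cluster per month and gives no derivation.

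**The concern.** If the study criteria were the same as those for using T-MACS, a calculated score would be a fair stand-in for an eligibility check. Section 6.2 shows that they are not the same. A patient with little English can be risk-scored in routine care and so enters the list of eligible participants, although 6.2 excludes that patient. The same may happen with a patient who lacks capacity.

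The capacity criterion has a second problem. It is tied to written informed consent, while 6.3 adopts opt-out consent, under which a patient who does nothing is included. The two sections need reconciling.

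What is at stake is the denominator of a feasibility trial, where the denominator is much of the result. An overstated eligible count would carry into the planning of the full-scale trial. An understated completion proportion could make an eligibility problem look like a recruitment problem, when section 17 says that adjustments will follow from where the problem lies.

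**Working it through.** **Step 1: the passages side by side.**

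- Section 5.2: T-MACS was in routine use at both hospitals while neither was exposed to SDM. Ability to hold an SDM conversation therefore cannot have been a condition for calculating the score.
- Section 6.2: that ability is a condition for the study. So is capacity to give written informed consent, which is a research criterion.
- Section 6.3: the two sets of criteria are said to be identical. For English this cannot be right. For capacity it is not implied by anything in the protocol, which does not print the criteria for using T-MACS.

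**Step 2: does any later check remove such patients?** None is described.

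- In the intervention phase (section 5.2) the data are entered in the calculator, the aid is generated, and the conversation follows. The record that makes the patient eligible exists before the conversation to which the English criterion refers.
- The weekly cross-check in 6.3 compares the T-MACS database with the surveys in order to find opt-outs, not ineligible patients.
- Section 6.3 also treats a patient who does not engage in SDM as having opted out. A patient who should be excluded for language may thus be logged as an opt-out.

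**Step 3: size, for illustration.** The protocol has no figure to reproduce here: 200 to 300 per cluster-month is a bare estimate of eligible patients. Treat it as the number of T-MACS records. Let x be the share of records that fail 6.2; x is not in the protocol and is assumed.

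Records over the whole study: 200 × 2 clusters × 4 recruitment months = 1,600, and 300 × 2 × 4 = 2,400. At x = 5% to 15%, the ineligible records per cluster-month are 200 × 0.05 = 10 up to 300 × 0.15 = 45.

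Overstatement of the eligible count = 1/(1 − x).

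If no ineligible patient completes the survey, apparent completion = true completion × (1 − x). The true completion needed to show 50% = 0.50/(1 − x).

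| x (assumed) | Eligible count overstated by factor | True 55% reads as | True rate needed to show 50% |
|---|---|---|---|
| 5% | 1/0.95 = 1.05 | 0.55 × 0.95 = 52.3% | 52.6% |
| 10% | 1/0.90 = 1.11 | 0.55 × 0.90 = 49.5% | 55.6% |
| 15% | 1/0.85 = 1.18 | 0.55 × 0.85 = 46.8% | 58.8% |

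A true 55% reads as 50% when 0.55 × (1 − x) = 0.50, that is x = 1 − 0.50/0.55 = 9.1%.

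**Step 4: how far this depends on non-completion.** If ineligible patients complete at rate c, apparent completion = 0.55 × (1 − x) + c × x. With x = 10%:

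- c = 0 gives 49.5%.
- c = 27.5% gives 49.5% + 2.75% = 52.3%.
- c = 55% gives 49.5% + 5.5% = 55.0%, so the proportion is unchanged, although some of those counted should not be in the study.

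The overstatement of the eligible count does not depend on c.

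**The case against.** The strongest reply is that the consequences are modest and their size unknown. The share of ineligible records is nowhere in the protocol. The error in completion is in the cautious direction, and it disappears if ineligible patients complete as often as others. Missing green does not end the programme: under section 17, a mix of green and yellow leads to protocol adjustments, and even a single red may be rectifiable. All of this stands, and it is why the table is only illustrative and the point is not rated higher. It does not rescue the statement that the criteria are identical, or the overstated eligible count.

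It can also be said that clinicians may consider capacity before scoring, and that capacity for written consent can be judged without taking a signature. That is fair. The case is stronger for English than for capacity. For capacity, what is certain is that the wording does not fit opt-out consent.

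A reader might go further and infer that the English exclusion operates only in the SDM phase, so that the decisional-conflict comparison is biased in favour of SDM. The protocol does not support this. Section 6.2 applies the criterion to the whole study, and under the rule in 6.3 it removes nobody from the list in either phase. A clinician could also judge a patient's English during a control encounter. Nor can a bias be put in points on the decisional conflict scale. That would need ineligible patients among the control completers, the opposite of the assumption behind the table, and a score difference that the protocol does not give. Section 9.1 offers that comparison only as evidence towards proof of concept. What remains is an unquantified risk: the criterion is worded around a conversation that takes place only after crossover, so it may be applied differently in the two phases.

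**Conclusion.** The point holds as an internal contradiction that gives a wrong denominator. Section 6.3 infers eligibility from a T-MACS score on a ground that section 6.2 contradicts, and no described step corrects the list.

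The direction for the number of eligible participants per month follows from the text: it is overstated if any record fails 6.2. The recruitment rate and the survey-completion criterion are understated to the extent that the ineligible patients do not complete the survey. The size is unknown. The result that a true 55% completion drops below the green line at about 9% ineligible assumes that none of those patients completes.

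This should be fixed, and before recruitment starts, because eligibility that was not recorded at the time cannot be reliably reconstructed afterwards.

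**What to change.** 1. In 6.3, delete the statement that the criteria are identical, and call the T-MACS database a list of screened patients.
2. Reconcile the written-consent wording in 6.2 with the opt-out process in 6.3.
3. Word the two criteria so that they depend neither on phase nor on survey completion. For example: able to understand the information sheet and discuss their care in English; has capacity to decide on taking part. Ability to complete the survey should not be a criterion. That would be partly circular in the denominator for survey completion and would hide language-related non-completion, which is itself feasibility information.
4. Record both criteria as yes/no on the CRF for every T-MACS record, in both phases, and before the aid is generated in the intervention phase. The CRF is the practical place, because the calculator update is planned only for the transition stage.
5. Log patients who fail a criterion as ineligible, separately from opt-outs.
6. Report T-MACS records, eligible patients and survey completers separately, by cluster and phase, and use eligible patients as the denominator in section 17.

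The cost is two extra fields per record, a small data-entry burden for clinicians, a wording change in 6.2 and 6.3, and a somewhat smaller eligible count.
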